10.3 Methods and Timing for Capturing and Assessing Safety Parameters

10.3.1 Adverse Event Reporting Period

The study AE reporting period is as follows: After informed consent but prior to initiation of study treatment, only SAEs associated with any protocol-imposed interventions will be reported. After informed consent is obtained and the first administration of study drug, the reporting period for all non-serious AEs and SAEs begins and continues for approximately 5 years or until study discontinuation/termination, whichever is longer. The criteria for determining, and the reporting of SAEs is provided in Section 10.2.

10.3.2 Eliciting Adverse Events

Investigators will seek information on AEs, SAEs, and EOSI at each subject contact by specific questioning and, as appropriate, by examination. Information on all AEs and SAEs

and EOSI, should be recorded in the subject's medical record and on the AE Case Report Form (eCRF).

10.3.3 Assessment of Seriousness, Severity, and Causality

The Investigator responsible for the care of the subject or medically qualified designee will assess AEs for severity, relationship to study drug, and seriousness (refer to Section 10.2 for SAE definitions). These assessments must be made by a study clinician with the training and authority to make a diagnosis (eg, MD/DO, physician's assistant, nurse practitioner, or DDS).

10.3.3.1 Seriousness

The investigator will assess if an AE should be classified as "serious" based on the seriousness criteria enumerated in Section 10.2. Seriousness serves as a guide for defining regulatory reporting obligations.

10.3.3.2 Severity

Severity (as in mild, moderate, or severe headache) is not equivalent to seriousness, which is based on subject/event outcome or action criteria usually associated with events that pose a threat to a subject's life or functioning. The severity of each will be assessed using the defined categories in Table 10.3.3.2.1.

The Investigator will determine the severity of each AE and SAE and EOSI using the NCI CTCAE v4. Adverse events that do not have a corresponding CTCAE term will be assessed according to the general guidelines for grading used in the CTCAE v4 as stated below.

Grade	Description	
1	Mild: asymptomatic or mild symptoms; clinical or diagnostic observatio indicated	ns only; intervention not
2	Moderate: minimal, local or noninvasive intervention indicated; limiting age-appropriate instrumental activities of daily living (ADL) ^a	
3	Severe or medically significant but not immediately life-threatening: hospitalization or prolongation of hospitalization indicated; disabling; limiting self-care ADL ^b	
4	Life threatening or debilitating: consequences; urgent intervention indicated	Grade 4 and 5 AEs should always be
5	Death related to AE	reported as SAEs

 Table 10.3.3.2.1: Adverse Event Grading (Severity) Scale

^a Instrumental ADL refer to the following examples: preparing meals, shopping for groceries or clothes, using the telephone, managing money.

^b Self-care ADL refer to the following examples: bathing, dressing and undressing, feeding oneself, using the toilet, taking medications, not bedridden.

BIOMARIN	270-201 – Amendment 3	Page 57

10.3.3.3 Causality

The Investigator will determine the relationship of an AE to the study drug and will record it on the source documents and AE CRF. To ensure consistency of causality assessments, Investigators should apply the guidance in Table 10.3.3.3.1.

Relationship	Description
Not Related	• Exposure to the IP has not occurred
	• OR
	• The administration of the IP and the occurrence of the AE are not reasonably related in time
	• OR
	• The AE is considered likely to be related to an etiology other than the use of the IP; that is, there are no facts, evidence, or arguments to suggest a causal relationship to the IP.
Related	• The administration of the IP and the occurrence of the AE are reasonably related in time
	AND
	• The AE could possibly be explained by factors or causes other than exposure to the IP
	OR
	• The administration of IP and the occurrence of the AE are reasonably related in time
	AND
	• The AE is more likely explained by exposure to the IP than by other factors or causes.

Factors suggestive of a causal relationship could include (but are not limited to):

- Plausible temporal relationship
- Absence of alternative explanations
- Rarity of event in a given patient or disease state
- Absence of event prior to study drug exposure
- Consistency with study product pharmacology

- Known relationship to underlying mechanism of study drug action
- Similarity to adverse reactions seen with related drug products
- Abatement of AE with discontinuation of study drug, and/or recurrence of AE with reintroduction of study drug

The investigator's assessment of causality for individual AE reports is part of the study documentation process. Regardless of the Investigator's assessment of causality for individual AE reports, the Sponsor will promptly evaluate all reported SAEs against cumulative product experience to identify and expeditiously communicate possible new safety findings to investigators and applicable regulatory authorities.

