9.3.3.1 Study Safety Evaluation Criteria

If any of the following events occur in a subject in the study who has received BMN 270 infusion, enrollment into the trial will be put on halt to complete an extensive safety analysis per Section 9.1.

- A 5-fold increase from baseline in ALT after BMN 270 administration
- The occurrence of Grade 3 or higher adverse events assessed as related to study drug, including liver failure and clinical hepatitis
- Grade 2 adverse event assessed as related to study drug that persists for at least 7 days
- The detection of neutralizing antibodies to hFVIII following BMN 270 infusion
- The persistent detection of the AAV vector genome in the semen of a participant more than 26 weeks after BMN 270 infusion, as discussed in Section 9.7.8.5
- The occurrence of a malignancy excluding skin cancers at any point after BMN 270 infusion

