10.1.1 Adverse Events

For this protocol, a reportable adverse event (AE) is any untoward medical occurrence (e.g., sign, symptom, illness, disease or injury) in a subject administered the study-drug or other protocol-imposed intervention, regardless of attribution. This includes the following:

- AEs not previously observed in the subject that emerge during the course of the study.
- Pre-existing medical conditions judged by the Investigator to have worsened in severity or frequency or changed in character during the study.
- Complications that occur as a result of non-drug protocol-imposed interventions (eg, AEs related to screening procedures).

An adverse drug reaction is any AE for which there is a reasonable possibility that the study-drug caused the AE. "Reasonable possibility" means there is evidence to suggest a causal relationship between the study-drug and the AE.

Bleeding events that are normal events of haemophilia (ie, bleeding events which occur only because the subject is a haemophiliac) should not be recorded as AEs but will instead be captured in subject diaries. Bleeding events that occur where a normal (ie, non-haemophiliac) patient would bleed, such as bleeding as a result of major trauma, should be recorded as adverse events. All bleeding events which meet criteria for being serious should be reported as serious adverse events (SAEs) whether or not they are bleeding events that are normal sequelae of haemophilia.

Whenever possible, it is preferable to record a diagnosis as the AE term rather than a series of terms relating to a diagnosis.

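### The first limb of Related in the causality table never asks whether the study drug is a possible cause, and on most readings it overlaps Not Related with no rule for which row wins

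*Protocol*

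**What the plan says.** Section 10.3.3.3 asks investigators to apply Table 10.3.3.3.1 so that causality is assessed consistently. The table has two rows.

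- **Related** needs a reasonable time relation plus one of two limbs. Limb 1: "The AE could possibly be explained by factors or causes other than exposure to the IP". Limb 2: "The AE is more likely explained by exposure to the IP than by other factors or causes".
- **Not Related** applies if there was no exposure, if the time relation is not reasonable, or under a third limb: "The AE is considered likely to be related to an etiology other than the use of the IP". The third limb is then glossed: "there are no facts, evidence, or arguments to suggest a causal relationship to the IP".

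The list of factors suggestive of causality below the table includes a plausible time relation and also "Absence of alternative explanations".

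Section 10.1.1 defines an adverse drug reaction by a reasonable possibility of causation, which "means there is evidence to suggest a causal relationship between the study-drug and the AE".

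Section 9.3.3.1 halts enrolment on any of six events, two of which use relatedness. One is "The occurrence of Grade 3 or higher adverse events assessed as related to study drug"; the other is a related Grade 2 event lasting at least 7 days. Section 14.5 summarises AE incidence by relationship to study drug, among other factors. Section 9.7 makes safety the primary endpoint.

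**The concern.** Limb 1 looks like a tier for events that might be due to the IP even though something else could also explain them. The words that would say so are missing. As written, the condition is that another cause is possible, which on its own is a reason against attributing the event to the IP. It also runs against the list under the table, where having no other explanation counts towards causality.

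A likely other cause is also a possible one, so limb 1 can catch events that the third limb of Not Related is meant to remove. For example, take a Grade 2 event lasting 7 days that is thought likely to be due to prednisolone (given under 9.4.8.2), still reasonably close in time to the infusion, with nothing else pointing to the IP. Read by limb 1 it is Related and meets a halt criterion. Read by the third limb of Not Related it does not. At stake are the reproducibility of a halt trigger and of the related-AE counts in a first-in-human trial.

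**Working it through.** The plan has no figure to reproduce here: this is a classification rule, and 14.6 reports no formal sample size calculation. The check is whether the two rows can both apply to one event.

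**Step 1. List the possible events.** For an AE in a dosed subject, let T = reasonable time relation, P = another cause possible, O = another cause likely, M = the IP is the likelier cause, F = evidence for the IP other than timing. Drop the inconsistent combinations: O needs P; O and M exclude each other; M needs T; a timely event with no other possible cause has M. This leaves:

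- not timely: 3 combinations of P and O × 2 values of F = 6
- timely: 4 combinations of P, O and M × 2 values of F = 8
- total 6 + 8 = 14 states

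**Step 2. Apply the rows.** Related = T and (P or M). Not Related = not T, or the third limb. The third limb can be read in three ways.

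| Reading of the third limb | States in both rows | Which |
|---|---|---|
| A: another etiology is likely | 2 | timely, O, with or without F |
| B: A, and no evidence for the IP other than timing | 1 | timely, O, no F |
| C: A, and no evidence at all, with timing counted as evidence | 0 | none |

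Under C the overlap goes, but the third limb then excludes no timely event and adds nothing to the limb on time relation.

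**Step 3. See what Related requires.** Under all three readings, all 8 timely states meet Related. If another cause is possible, limb 1 is met; if none is, limb 2 is. Taken literally, a reasonable time relation is sufficient by itself.

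**Step 4. Compare with 10.1.1.** Two timely states are Related although the IP is not the likelier cause and no evidence beyond timing points to it (another cause possible but not likely; another cause likely). Limb 1 is therefore looser than the adverse drug reaction standard, unless timing alone is accepted as evidence there too.

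**Step 5. Size.** Inputs: up to 12 subjects (14.6) and up to four per cohort (9.4.6.2). One subject coded the other way moves an incidence by 100/12 = 8.3 points overall, or 100/4 = 25 points in a full cohort. A single event of qualifying grade suffices for a halt. The documents give no rate for such ambiguous events. Assuming that a proportion p of subjects has one, the chance of at least one in n subjects is 1 − (1 − p)^n:

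| p (assumed) | n = 4 | n = 12 |
|---|---|---|
| 2% | 8% | 22% |
| 5% | 19% | 46% |
| 10% | 34% | 72% |
| 20% | 59% | 93% |

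**The case against.** The strongest reply is the gloss on the third limb of Not Related. It can be read as defining that limb, and a plausible time relation is the first factor listed under the table. A timely event then always has an argument in favour of the IP, falls outside the third limb, and cannot be in both rows. This is reading C, and it is tenable. A reader might infer from the table that one event can be classed both ways on any reading; the documents do not support that. What remains is that reading C leaves the third limb empty for timely events, and that limb 1 still omits the IP as a possible cause.

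A reader might also infer that the table contradicts 10.1.1. It does not do so directly. That section defines an adverse drug reaction, whereas the halt criteria and the AE summary refer to relatedness to study drug, which the table governs. These are two causality standards of different strictness, not two definitions of one term.

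The consequences are also bounded. The table is guidance for a qualified clinician. The sponsor evaluates all reported serious events whatever the investigator's causality call (10.3.3.3), and the Data Review Board reviews safety continuously (Section 15). The 5-fold ALT rise, neutralizing antibodies, persistent vector in semen and malignancy halt enrolment without reference to relatedness. The literal wording errs towards Related, so the likelier error is a precautionary pause and not a missed signal. All of this stands and limits the point, but it does not repair limb 1.

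**Conclusion.** The concern holds in a limited form. Limb 1 of Related is mis-stated: it is met by any timely event that could have another cause, with no requirement that the IP could be a cause. On two of the three readings of the third limb of Not Related, some timely events with a likely other cause fall in both rows, and the table does not say which row prevails. The third reading avoids this only by emptying that limb for timely events.

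The effect is confined to two of the six halt criteria and to the AE summary by relationship. The shifts of 8.3 and 25 points are what any recoding of one subject would cause in a trial of this size. They are not evidence that this wording has caused or will cause recoding. The 25 points need a full cohort of four, which 9.4.6.2 does not guarantee, and either shift needs a subject with no other related event in the same category. The ambiguous-event rates in the working are assumptions.

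The text assessed is that of Amendment 3, the latest version in the part of the protocol at hand. The same table stands in the earlier versions there. The remaining parts are not shown.

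**What to change.** 1. Reword limb 1 of Related: *reasonably related in time AND exposure to the IP is a possible explanation, even though other factors or causes could also explain the AE*.
2. Make the third limb of Not Related require both a likely other etiology and the absence of any fact, evidence or argument for the IP.
3. State whether timing alone counts as such an argument. If it does, the third limb reaches no timely event, and a timely event for which the IP is not a possible explanation would fit neither row. Stating that timing alone does not count avoids this.
4. Add that an AE meeting both rows is coded Related. Without this, a timely event with a likely other cause, the IP not excluded and no evidence for it would still meet both reworded rows. The rule makes the final coding exclusive and keeps the conservative default.
5. State how Related maps to the adverse drug reaction standard in 10.1.1.

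The cost is the wording of one table and the matching CRF completion guidance, plus one review of events already coded. The halt criteria themselves do not change.

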10.4 Procedures for Recording Adverse Events

10.4.1 Recording Adverse Events on a eCRF

Investigators should use precise medical terminology when recording AEs or SAEs on the AE eCRF. Avoid colloquialisms and abbreviations.

Record only one diagnosis, sign, or symptom per event field on the AE eCRF (eg, nausea and vomiting should not be recorded in the same entry, but as 2 separate entries).

In order to classify AEs and diseases, preferred terms will be assigned by the Sponsor to the original terms entered on the AE eCRF, using MedDRA (Medical Dictionary for Regulatory Activities) terminology.

10.4.1.1 Diagnosis versus Signs and Symptoms

Using accepted medical terminology, enter the diagnosis (if known). If not known, enter sign(s) and/or symptom(s). If a diagnosis subsequently becomes available, then this diagnosis should be entered on the AE eCRF, replacing the original entries where appropriate.

10.4.1.2 Adverse Events Occurring Secondary to Other Events

In general, AEs occurring secondary to other events (eg, cascade events) should be identified by their primary cause. For example, if severe diarrhea is known to have resulted in dehydration, it is sufficient to record only diarrhea as an AE or SAE on the AE eCRF. However, medically important events that may be linked and/or separated in time should be recorded as independent events on the AE eCRF. For example, if severe haemorrhage leads to renal failure, both events should be recorded separately on the AE eCRF.

10.4.1.3 Persistent or Recurrent Adverse Events

A persistent AE is one that extends continuously, without resolution, between subject evaluation time points. Such an event should be recorded only once on the AE eCRF unless its severity increases or decreases (in which case it should be recorded again on the AE eCRF).

A recurrent AE is one that occurs and resolves between subject evaluation time points, but then subsequently recurs. All recurrences of the AE should be recorded on the AE eCRF.

10.4.1.4 Abnormal Laboratory Values

Laboratory test results will be recorded on the laboratory results pages of the AE eCRF, or appear on electronically produced laboratory reports submitted directly from the central laboratory, if applicable.

Any laboratory result abnormality fulfilling the criteria for a SAE should be reported as such, in addition to being recorded as an AE in the AE eCRF.

A clinical laboratory abnormality is considered clinically significant and should be documented as AE if **any** of the following conditions is met:

- Accompanied by clinical symptoms
- Leading to a change in study medication (e.g. dose modification, interruption or permanent discontinuation)
- Requiring a change in concomitant therapy (e.g. addition of, interruption of, discontinuation of, or any other change in a concomitant medication, therapy or treatment).
- The laboratory abnormality persists upon repeat confirmatory testing.
- The abnormality suggests a disease and/or organ toxicity
- The abnormality is of a degree that requires active management (eg, change of dose, discontinuation of study drug, more frequent follow-up assessments, further diagnostic investigation, etc.)

This applies to any protocol and non-protocol specified safety and efficacy laboratory result from tests performed after the first dose of study medication that falls outside the laboratory reference range and meets the clinical significance criteria.

This does not apply to any abnormal laboratory result that falls outside the laboratory reference range but that does not meet the clinical significance criteria (these will be analyzed and reported as laboratory abnormalities), those that are considered AEs of the type

explicitly exempted by the protocol, or those which are a result of an AE that has already been reported.

For purposes of this study, laboratory tests showing a decreased level of hFVIII activity should not be reported as adverse events unless signs of worsening are observed.

10.4.1.5 Pre-existing Conditions

A pre-existing condition is one that is present prior to administration of BMN 270. Such conditions should be recorded as medical history on the appropriate eCRF.

A pre-existing condition should be recorded as an AE or SAE during the study **only** if the frequency, intensity, or character of the condition worsens during the study period. It is important to convey the concept that a pre-existing condition has changed by including applicable language in the verbatim description of the event (eg, *more frequent* headaches).

10.4.1.6 General Physical Examination Findings

At screening, any clinically significant abnormality should be recorded as a pre-existing condition (refer to Section 10.4.1.5). During the study, any new clinically significant findings and/or abnormalities discovered on physical examination that meet the definition of an AE (or an SAE) must be recorded and document as an AE or SAE on the AE eCRF.

10.4.1.7 Hospitalization, Prolonged Hospitalization, or Surgery

Any AE that results in hospitalization or prolonged hospitalization should be documented and reported as an SAE unless specifically instructed otherwise in this protocol (refer to Section 10.2).

There are some hospitalization scenarios that do not require reporting as an SAE when there is no occurrence of an AE. These scenarios include planned hospitalizations or prolonged hospitalizations to:

- Perform a protocol-mandated efficacy measurement
- Undergo a diagnostic or elective surgical procedure for a pre-existing medical condition that has not changed
- Hospitalization solely for the purpose of insertion of an in-dwelling IV catheter (such as a Port-a-Cath or other brand) for administration of study drug will not be considered an SAE.
- Receive scheduled therapy (study drug or otherwise) for the study indication

10.4.1.8 Deaths

All deaths that occur during the AE reporting period (refer to Section 10.3.1), regardless of attribution, will be recorded on the AE eCRF and expeditiously reported to the Sponsor as an SAE.

When recording a death, the event or condition that caused or contributed to the fatal outcome should be recorded as the single medical concept on the eCRF. If the cause of death is unknown and cannot be ascertained at the time of reporting, record "Unexplained Death" or "Death of Unknown Cause" on the AE eCRF.

10.4.1.9 Pregnancy

Although not an AE per se, pregnancy in the partner of a subject taking trial medication should be reported expeditiously to the Sponsor to facilitate outcome monitoring by the Sponsor. Pregnancy in partner should be reported during the period up to 5 years after viral infusion.

Pregnancy in partner should be reported within 24 hours of the site becoming aware of the pregnancy by entering the information on the Pregnancy eCRF and submitting to BPV within 24 hours of the site becoming aware of the event. The Investigator must make every effort to follow the subject's partner through resolution of the pregnancy (delivery or termination) and to report the resolution on the Pregnancy Follow-up Form in the study reference materials. In the event of pregnancy in the partner of a study subject, the Investigator should make every reasonable attempt to obtain the woman's consent for release of protected health information.

Abortion, whether therapeutic or spontaneous, should always be classified as an SAE (as the Sponsor considers these to be medically significant), recorded on the AE eCRF, and expeditiously reported to the Sponsor as an SAE.

